### 8.2 Evaluation of Non-Objective Related Characteristics

#### 8.2.1 Disposition of Subjects

Subject disposition will be tabulated by cohort (see 2.7) including the variables listed in 6.1. Subjects will be allocated on each treatment regimen depending on if they were screened before or after the IA. The analysis will be repeated per site. A flow-chart detailing the number of subjects at the different stages will be prepared. The number and percentage of subjects per visit/cycle will be summarised in a further table. Subjects withdrawn from the study will be listed along with the primary reason for discontinuation. In addition, the primary reason for withdrawal will be tabulated. Exclusion from analysis sets as well as the reason(s) for exclusion will be listed. A table detailing the number of subjects per visit will additionally be provided.

Table	
14.1.1	Subject disposition by site and overall
14.1.2	Visit/cycle attendance
Figure	
14.1.1	Disposition flow chart
Listing	
16.1.1	Informed consent information, Screening failure, Enrolment, Treated

16.1.2	Visit dates and withdrawals
16.1.3	Protocol deviations and other reasons for exclusion from analysis sets, assignment to analysis sets

### 8.2.2 Demographics and other baseline characteristics

Demographic and baseline characteristics (see section 6.1) will be summarized by treatment cohort (see 2.7) using summary statistics (see section 8.1) for continuous variables (age, ECG) or absolute and relative frequencies (n, %) for categorical variables (Gender, Race, IPSS-R score, WHO Classification). Results will be presented by FAS and, if the analysis sets differ more than 10% between the number of included subjects, will be presented also for the other analysis sets (SES, PPS).

Table	
14.2.1	Demographics and body measurements
14.2.2	Baseline characteristics (continuous)
14.2.3	Baseline characteristics (categorical)
Listing	
16.2.1	Demographics
16.2.2	WHO classification
16.2.3	IPSS-R score
16.2.4	ECG

### 8.2.3 Medical History, Concomitant Diseases/Procedures, Previous and Concomitant Medication

Absolute and relative frequencies (n, %) of concomitant disease will be summarized based on MedDRA system organ class (SOC) and preferred term (PT) levels for the SES.

Absolute and relative frequencies (n, %) concomitant medication and MDS/AML specific concomitant medication will be summarized based on Anatomical Therapeutic Chemical (ATC) Classification code levels 2 and 3 for the SES.

Absolute and relative frequencies (n,%) of MDS/AML related Medical History will be summarized for the SES.

All results will be presented by cohort (see 2.7).

Table	
14.3.1	Concomitant diseases by SOC and PT
14.3.2	MDS/AML related history
14.3.3	Concomitant medications by ATC levels
14.3.4	MDS/AML specific concomitant Medication by ATC levels
Listing	
16.3.1	Concomitant diseases
16.3.2	MDS/AML related history
16.3.3	Concomitant Medication
16.3.4	MDS/AML specific concomitant Medication
16.3.5	Medical history
16.3.6	Prior MDS/AML specific medication

### 8.3 Evaluation of Primary Endpoint

The primary objective of this study is to assess the efficacy of imetelstat for the treatment of AML and MDS patients failing or being refractory to first line hypomethylating agent (HMA)-based treatment. This should be illustrated by testing the hypothesis stated in section 2.5 using the primary endpoint stated in section 6.2.1 (see 7.7.4 for derivation).

The absolute and relative frequencies of overall hematological response as assessed in week ■ (beginning of ■) of treatment with imetelstat will be evaluated using the FAS and repeated for the PPS if the analysis sets differ more than 10% between the number of included subjects. Treatment success will be determined by patients showing at least PR (CR, CRi or PR) and/or showing a hematologic improvement for one or several lines.

The primary analysis will be based on a Simon's two-stage design for an initial assessment of efficacy. Based on the study hypothesis (see section 2.5), an absolute cut-off value of ■ subject out of ■ will be used to determine if the study must be stopped for futility at the IA. For the final analysis in case the study proceeds, if final sample size is equal to the calculated one, a cut-off value of ■ subjects out of ■ will be fixed.

If final sample size is different from the calculated sample size (overrunning), uniformly minimum variance unbiased estimator UMVUE will be tested (see Melikov M. & Karanevich A. 2022) with a

model based on a binomial distribution conditioned to the first stage results and with an assumed expected true response rate of 0.2.

A SAS macro (based on source <https://www.lexjansen.com/pharmasug/2022/SA/PharmaSUG-2022-SA-123.pdf>) can be used for this analysis (see Appendix 11.4)

For the IA:

A binomial exact test will be performed with a two-sided 90% confidence interval for overall hematological response rate using the Clopper-Pearson method. A SAS pseudo code can be:

```
proc freq data=Data;
  tables Hematological_response / binomial(all level="0") alpha=0.1 cl ;
  exact binomial /point;
run;
```

For the final analysis:

The final analysis was going to be performed with a calculation of the p-value and a 90% confidence interval (two-sided, equivalent to a one-sided 95% confidence interval) for the UMVUE (see Melikov M. & Karanevich A. 2022).

Due to the transient improvement seen in WBC and peripheral blasts in patients early in treatment, it was accorded to continue the study in an exploratory approach with a change in dose frequency. Therefore, binomial test will be performed with a two-sided 90% confidence interval for overall haematological response rate using the Clopper-Pearson method for both treatment cohorts (see 2.7) independently. Analysis will be repeated by subgroups (see 4.2). A SAS pseudo code can be:

```
proc freq data=Data;
  by Treatment_cohort;
  tables Hematological_response / binomial(all level="0") alpha=0.1 cl ;
  exact binomial /point;
run;
```

Response assessments of visit 5(W9 C3) and visit 9(W17 C5) will be listed.

Table	
14.5.1	Overall hematological response rate
Figures	
14.5.1	Overall hematological response rate at beginning of cycle 5
Listing	
16.5.1	Response assessment

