10.1 General statistical considerations

No confirmatory statistical analysis will be conducted due to the changes described in section 5 and section 7.1. All analysis will be only explorative.

Statistical analysis will be performed using SAS® version 9.4 or higher.

Summary statistics (arithmetic mean, standard deviation, median, minimum, and maximum for quantitative variables) will be presented by the treatment group. Frequency tables for categorical data will be provided. Medical history findings will be summarized using MedDRA terms.

Missing values will not be imputed. Outliers will be identified prior to the analyses of the efficacy endpoints and have to be checked by the study physician. According to the decision of the data management, the statistician and the study physician, outliers will be kept in the database or set to "missing".

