10.3 Sample size calculation

The study was designed as single-arm phase II trial. The design of the trial focused on demonstrating that the efficacy is greater than an undesired level of efficacy (p_0) which would indicate that the treatment is ineffective. A Simon's two-stage design was used to allow for initial assessment of efficacy. The sample size calculation was based on the following assumptions.

- Given Null hypothesis $H_0: p \leq p_0$
- Alternative hypothesis $H_1: p > p_0$
- Level of inefficacy $p_0 = 0.05$
- Expected true response rate $p_1 = 0.2$
- Type-1-error $\alpha = 0.05$, one-sided
- Type-2-error $\beta = 0.1$

The null hypothesis that the true response rate is 0.05 was planned to be tested against a one-sided alternative. In the first stage, 10 patients were accrued. If there were 1 or fewer responses in these 10 patients, the study should be stopped. Otherwise, it was planned to accrue 10 additional patients for a total of 20. The null hypothesis would be rejected in favor of the alternative hypothesis if 5 or more responses are observed in 20 patients. This design yielded a one-sided type I error rate of no more than 0.05 and power of at least 0.9 when the true response rate is 0.2. To account for a loss of follow up of ~10%, enrollment of up to 22 patients is expected. Similarly, a total of 22 patients were planned to be enrolled prior to the interim analysis to ensure 20 evaluable patients for the interim analysis.

██████████ Due to potential benefits for the patients, the study will continue in an exploratory approach with change dose frequency as described in section 7.1.

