### 11.4 Appendix 4: SAS Macro

```
%macro Simon_KC (num_success=, n1=21, n=41, r1=1, rt=5, p0=0.1, n2star=,
x1=, alpha=0.1);
    data pval (keep= umvue cpval calpha p_val ord);
        num1=0;
        denom1=0;
        do X1=max((&r1+1), (&num_success-&n2star)) to min(&num_success,&n1);
            num0=comb(&n1-1, x1-1)*comb(&n2star, &num_success-x1);
            num1=num1+num0;
            denom0=comb(&n1, x1)*comb(&n2star, &num_success-x1);
            denom1=denom1+denom0;
            UMVUE=round(num1/denom1, 0.0001);
            /* output; */
        end;
        /*conditional p-value of stage 2 */
        cpval = round(1-CDF('BINOMIAL', (&num_success-&x1)-1, &p0,
&n2star), 0.0001);
        /*conditional type I error of stage 2 */
        calpha = round(1-CDF('BINOMIAL', (&rt+1)-(&x1)-1, &p0, &n-&n1),
0.0001);
        /*finding pstar*/
        pstar=round(betainv(cpval, (&rt+1)-&x1, (&n-&n1)-((&rt+1)-&x1)+1),
0.0001);
        /* function calculating p-value using KC equation (7) */
        p_val=0;
        do X1=&r1+1 to &n1;
```

```

        X2 = (&rt+1) - X1; /*To generalize the macro possible val-ues
        of X2 should be based on rt*/
        pr_x = PDF('BINOMIAL', X1, &p0, &n1)*(1-CDF('BINOMIAL', X2- 1,
        pstar, &n-&n1));
        p_val =round(p_val+pr_x, 0.0001);
        /* output; */
    end;
    ord=1;
    run;

    /* A confidence interval and a reasonable point estimate */
    data confint (keep= ord p0prime );
    p_val=0;
    p0prime=0;
    do clevel = &alpha/2, 0.5, 1-(&alpha/2);
    do while (p_val < clevel) ;
    p0prime = p0prime + 0.0001;
    /*conditional p-value of stage 2 for each incrementally increasing
    p0prime */
    cpval = round(1-CDF('BINOMIAL', (&num_success-&x1)-1, p0prime,
    &n2star), 0.0001);
    /*pstar for each incrementally increasing p0prime */
    pstar=round(betainv(cpval, (&rt+1)-&x1, (&n-&n1)-((&rt+1)-&x1)+1),
    0.0001);
    /* function calculating p-value using KC equation (7)*/
    /* KC noted that pstar changes with different p0prime*/
    /* the function below is simultaneously evaluated with p0prime and
    cor-responding pstar */
        do X1= &r1+1 to &n1;
            X2 = (&rt+1) - X1;
            pr_x = PDF('BINOMIAL', X1, p0prime, &n1)*(1-
            CDF('BINOMIAL', X2-1, pstar, &n-&n1));
            p_val =p_val+pr_x;
            if x1=&r1+1 then p_val=pr_x;
            /* output; */
        end;
    end;
    ord=1;
    output;
    end;
    run;

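### The SAP's sample code for the primary endpoint names no null value, so it tests 0.5 instead of the protocol's 0.05, and it selects level 0 without saying what 0 means

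*SAP*

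**What the plan says.** For the final analysis, SAP 8.3 states that a "binomial test will be performed with a two-sided 90% confidence interval for overall haematological response rate using the Clopper-Pearson method for both treatment cohorts". The sample code that follows, like the interim code earlier in the same section, contains "tables Hematological_response / binomial(all level='0') alpha=0.1 cl" and "exact binomial /point". It gives no null proportion. The coding of the response variable is not stated there or in SAP 6.2.1, which names only the eCRF item it comes from.

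Protocol 10.3 supplies the reference value: "The null hypothesis that the true response rate is 0.05 was planned to be tested against a one-sided alternative". Protocol 10.1 now says "No confirmatory statistical analysis will be conducted due to the changes described in section 5 and section 7.1", and protocol 10.8.1 asks only for summary statistics and an exact two-sided 90% Clopper-Pearson interval.

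SAP 8.3 also keeps a UMVUE branch for a final sample size that differs from plan, "with an assumed expected true response rate of 0.2". SAP section 9 still describes this branch as an extension of the planned analysis. The macro in SAP 11.4 has the defaults "n1=21, n=41, r1=1, rt=5, p0=0.1".

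**The concern.** The sample code does not carry out the test that the prose describes. With no null supplied, PROC FREQ compares the selected level with 0.5. A test against 50% answers no question posed in protocol 10.3, where the uninteresting rate is 5% and the hoped-for rate is 20%. The level option adds a second problem. Under the common convention that 0 means no event, the procedure reports the share of patients who did not respond.

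The SAP describes itself as the guide for statistical programming, and Table 14.5.1 is its only primary-endpoint table. The zero-responder case is also real: the SAP's document history records that the interim data showed no responders, and the final code is run on both cohorts. Followed literally, the code could attach a very small p-value to the cohort in which nobody responded.

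**Working it through.** **Inputs.** From protocol 10.3: null 0.05, target rate 0.2, one-sided alpha 0.05, 20 evaluable patients intended for the interim, and a first-stage size of 10 also printed. From SAP 8.3: level 0, no null value, 90% interval. From software behaviour, not from the documents: the default null is 0.5. Assumed for the first table: 0 = non-responder.

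**Formulas.** With x responders among n patients:
- p from the code (one-sided): P(Y ≥ n − x), Y ~ Bin(n, 0.5). The two-sided exact p is twice this.
- p against the protocol null: P(X ≥ x), X ~ Bin(n, 0.05).

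**Results at n = 20, exact, one-sided.**

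| Responders | Code (level 0 vs 0.5) | Response rate vs 0.05 |
|---|---|---|
| 0 | 9.5e-7 | 1.00 |
| 1 | 2e-5 | 0.64 |
| 4 | 0.006 | 0.016 |
| 5 | 0.021 | 0.0026 |
| 6 | 0.058 | 0.0003 |

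For 0 responders the code's value is 0.5^20 = 9.5e-7, or 1.9e-6 two-sided.

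**How far the zero-responder result depends on n.** The code gives 0.5^n one-sided.
- n = 10: 0.00098 one-sided, 0.00195 two-sided.
- n = 13: 0.00012 one-sided. n = 14: 0.00006 one-sided, 0.00012 two-sided. n = 15: 0.00006 two-sided.

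So p < 0.0001 needs at least 14 patients one-sided or 15 two-sided.

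**Interval.** For 0/20 the exact 90% limits for response are 0 and 1 − 0.05^(1/20) = 0.139. The code's limits for level 0 are 0.861 and 1, the exact mirror image.

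**Other coding.** If 0 = responder, the rate and interval are right but the null is still 0.5. A cohort at the design's target, 4/20 = 20%, would give P(X ≤ 4 | 20, 0.5) = 0.006 and look significantly low.

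**Leftover two-stage material.** The plan's stated operating characteristics are type I error at most 0.05 and power at least 0.9. The sizes printed in protocol 10.3 (10 then 20, stop at 1 or fewer, reject at 5 or more) give 0.0022 and 0.334, so the stated power does not reproduce from them. The macro's n1 = 21, r1 = 1, n = 41 with rejection at 5 or more gives 0.0457 and 0.902, which does meet the stated targets. The macro rejects at rt + 1, so its default rt = 5 means 6 or more, with 0.0145 and 0.836. Its default p0 = 0.1 is twice the protocol null, and the 0.2 named in the text is the target rate, not the null. As an illustration, 5 responses in 41 with 2 in stage 1 gives p = 0.335 with the defaults and 0.046 with p0 = 0.05 and rt = 4.

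**The case against.** The fair case for leaving this alone has four parts. The code is offered as pseudo code, production programs are checked by a second programmer, and the table shells are separate documents, so nothing available shows that Table 14.5.1 will print the PROC FREQ p-value. The analysis is exploratory, and no cut-off or decision hangs on the p-value. If the interval is for non-response, one minus its limits recovers the right one, and a rate near 100% in a cohort known to have no responders would be noticed. SAP 8.3 refers to a hypothesis in SAP 2.5, which is not in the text available for this review, so the prose may point to the right null. All of this stands and lowers the severity. It does not make the code right: the second programmer validates against the same SAP, and the code contradicts protocol 10.3 under either coding.

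Three stronger readings are tempting and are not supported:
- A reader might infer that the p-value simply runs backwards and turns non-significant once the drug works. That needs the assumed coding, and even then 5/20 still gives 0.021. The curve is U-shaped around 50%: 15/20 again gives 0.021.
- A reader might infer that any cohort with no responders yields p < 0.0001. The size of cohort 2 is blacked out, and the MDS and AML subgroups may hold fewer than 14 patients.
- A reader might infer that the macro will produce a wrong final result. Its defaults can be overridden in the call, and SAP 8.3 words that analysis as superseded.

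**Conclusion.** The concern holds as a should-fix. The sample code in SAP 8.3 gives no null value and therefore tests 0.5 where the protocol's null is 0.05, whichever way the response variable is coded. If 0 means non-responder, it also reports the wrong proportion, and 0/20 gives 9.5e-7 one-sided against a correct 1.00. This rests on two things outside the documents, the PROC FREQ default and (for the reversal only) the coding of 0, and on taking the null from protocol 10.3 because SAP 2.5 could not be read.

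The documents do not support a claim that the trial could be declared positive by this route: confirmatory testing has been withdrawn. What is at risk is the clarity of the one primary-endpoint table. The two-stage remnants are a secondary matter of tidiness.

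**What to change.** Preferred: bring SAP 8.3 into line with protocol 10.8.1. Report the number and proportion of responders per cohort with the exact 90% Clopper-Pearson interval, drop the test and its p-value, and state the coding of the response variable.

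If a descriptive p-value is wanted, select the responder level, set the null to 0.05, and add a rule for a cohort or subgroup with no responders, since the responder level then does not occur in the data.

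Clean-up: state in SAP 8.3 and section 9 that the UMVUE and overrunning text and the macro in 11.4 no longer apply. If they are kept as live text, replace 0.2 by the null of 0.05, set p0 = 0.05 and set rt = 4 so that rejection is at 5 or more.

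The cost is a few sentences and one line of code in a SAP update before database lock. No data collection or protocol change is needed.

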## 8.4 Evaluation of Secondary Endpoints

Analyses of secondary endpoints will be performed in exploratory manner based on the FAS.

All results will be presented by treatment cohort (see 2.7).

### 8.4.1 Overall survival

Overall Survival (OS) as defined in 7.7.5 will be assessed using Kaplan-Meier method. The death of patient is regarded as the event of interest. The estimates obtained are invariably expressed in graphical form. Median survival time, the survival rate at week ■ (in ■■■■■) and for the overall study data at data hard lock with two-sided 95% confidence intervals (CI) using the complementary log-log transformation method will be tabulated.

The following pseudo-SAS code can be used defining Status = 0 as Censored and Status = 1 as event:

```
proc lifetest data=Data plots=survival(cb=hw test atrisk);
    time OverallSurvival*Status(0);
run;
```

Table	
14.6.1	Overall survival
Figures	
14.6.1	Overall survival

### 8.4.2 Progression-free-survival

Kaplan-Meier method will be used to assess progression-free survival (PFS) as defined in 7.7.6. Kaplan-Meier Curves depicting PFS will be generated. Additionally, median PFS, PFS rate at week ■ (in ■■■■■) and for the overall study data at data hard lock will be reported. The two-sided 95% confidence intervals (CI) for the median, and PFS rates will be calculated using the complementary log-log transformation method.

A similar pseudo-SAS code as in 8.4.1 can be used.

Table	
14.6.2	Progression-free survival
Figures	
14.6.2	Progression-free survival

### 8.4.3 Response related endpoints

#### Duration of response

Kaplan-Meier method will be used to assess duration of the response (see section 7.7.7 for deviation) will be summarised using descriptive methods described in section 8.1.

Table	
14.6.3	Duration of response

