10.8.2.3 Duration of response

Median time and 95% confidence interval for duration of response will be summarized using descriptive methods.

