#### 7.7.7 Duration of response

Duration of response (DoR) will be measured from the time measurement criteria are met for CR, CRi, PR, MLFS or SD (whichever is first recorded, defined in section 11.2 Appendix 2 a)) until the first date at which recurrent or progressive disease is objectively documented for patients with confirmed CR, CRi, PR, MLFS or SD criteria met. Therefore:

DoR [days] = first date with PD response criteria after response – date of CR, CRi or PR response criteria +1

If there was no progressive disease documented, subject will be censored on last documented response assessment:

DoR [days] = date of last response assessment – date of CR, CRi or PR response criteria +1

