## 8. Statistical Analysis Methods

### 8.1 Descriptive Statistics

The default summary statistics for quantitative variables will be the number of non-missing observations (n) and the number of missing observations (miss) as well as arithmetic mean, standard deviation (STD), minimum (min), median, and maximum (max).

For categorical variables, the number (n) and percentage (%) of subjects per category will be the default summary presentation, and, if applicable, the number of missing values is provided in a “missing” category. For the number of missing values, all subjects in the respective study population will be counted. Percentages will be calculated using a denominator of all subjects in a specified population with non-missing data. If necessary, the denominator will be specified in a footnote to the tables for clarification.

Visit related descriptive statistics will be provided only for visits with more than 5 non-missing observations. Results from visits with 5 or less non-missing observation will be only listed.

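### SAP 8.4.3 assigns duration of response both Kaplan-Meier and plain descriptive statistics; the descriptive version counts censored durations as complete and understates duration

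*SAP*

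**What the plan says.** SAP 8.4.3, for Table 14.6.3: "Kaplan-Meier method will be used to assess duration of the response (see section 7.7.7 for deviation) will be summarised using descriptive methods" of section 8.1. Two sentences seem to have been merged.

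Protocol 10.8.2.3: "Median time and 95% confidence interval for duration of response will be summarized using descriptive methods". Kaplan-Meier is not mentioned there, although protocol 10.8.2.1 and 10.8.2.2 name it for overall and progression-free survival.

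SAP 7.7.7 defines the variable. On censoring: "If there was no progressive disease documented, subject will be censored on last documented response assessment". The censored patient receives a number on the same scale as an observed duration: "DoR [days] = date of last response assessment – date of CR, CRi or PR response criteria +1". The prose of 7.7.7 starts the clock when "criteria are met for CR, CRi, PR, MLFS or SD (whichever is first recorded"); the formula lines below it name only CR, CRi or PR.

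SAP 8.1 lists, besides counts of observed and missing values, "arithmetic mean, standard deviation (STD), minimum (min), median, and maximum (max"). It contains neither event status nor a confidence interval. SAP Appendix 1 lists figures for overall and progression-free survival but none for duration of response.

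**The concern.** A programmer could fill Table 14.6.3 either way and defend the choice from the text. The results would differ materially. Kaplan-Meier uses the censoring that 7.7.7 defines. The 8.1 summary cannot: a patient still in response at the last assessment is treated as having lost response that day. The more patients who are still responding, the more the reported duration measures length of follow-up. The 8.1 route also cannot deliver the interval that the protocol asks for. At stake is a secondary efficacy figure that readers of a single-arm trial will compare with other agents.

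**Working it through.** The documents state no expected duration, precision or event count, so there is no figure of theirs to reproduce.

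**Inputs from the documents**
- Primary-phase assessments: "Response assessments of visit 5(W9 C3) and visit 9(W17 C5) will be listed" (SAP 8.3). Protocol VII, Part 1 puts these visits on study days 57 and 113.
- Non-responders stop after visit 9 (SAP 2.1). The Part 3 schedule has no response-assessment row, and assessments in Part 2c are optional.
- A continued responder's last evaluation is 6 months after the primary phase (protocol 5.1), taken as 182 days.
- The interim analysis found no responders (SAP document history); the planned response rate was 0.2 (protocol 10.3).

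**Assumptions, not from the documents:** exponential time to progression, 15 or 20 patients per analysis, and the assessment dates after visit 9.

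**A. Responders only (does not depend on how stable disease is handled).** The clock starts at visit 9 and ongoing responses are cut at 182 days. The visit grid and the +1 day are ignored.
- True median 360 days, so true mean = 360 / ln 2 = 519 days.
- Still in response at 182 days: exp(−182/519) = 0.704. More than half of the recorded values equal 182, so the crude median is **182**.
- Crude mean = 519 × (1 − 0.704) = **154** days.

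**B. Stable disease starts the clock (7.7.7 prose, protocol 2.3.2).** A patient qualifying at visit 5 and last assessed at visit 9 gets 113 − 57 + 1 = **57 days**, whether visit 9 shows progression (event) or not (censored). A patient with one qualifying assessment only gets 1 day.

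Suppose 15 patients qualify at visit 5 and none continues after visit 9. All have 57 days, so the crude median is 57. The share progressing by visit 9 is p = 1 − 2^(−56/m) for true median m. Kaplan-Meier reaches its median only with 8 or more events, so it is not reached with probability P(Bin(15, p) ≤ 7):

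| True median (days) | p | Crude median | Kaplan-Meier not reached |
|---|---|---|---|
| 60 | 0.476 | 57 | 57% |
| 120 | 0.276 | 57 | 97% |
| 240 | 0.149 | 57 | >99% |
| 480 | 0.078 | 57 | about 100% |

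**C. Some patients continue.** Simulation, 400 trials of 20 patients, 20% continuing after visit 9, no early loss, assessments 8 and 16 weeks after visit 9, follow-up ending 182 days after visit 9:

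| True median (days) | Censored | Crude median exactly 57 | Kaplan-Meier not reached |
|---|---|---|---|
| 42 | 33% | 100% of trials | 1% |
| 84 | 56% | 100% | 16% |
| 168 | 74% | 100% | 50% |
| 336 | 86% | 100% | 86% |

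The crude median leaves 57 in large samples only when most patients continue. With all continuing it is 113 days (true median 84) or 169 days (true median 168 or 336).

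**The case against.** The strongest reply is that Kaplan-Meier is evidently intended. SAP 8.4.3 names it first, a censoring rule has no purpose without it, and the protocol's request for an interval cannot mean the 8.1 list, which has none. The stray reference to 8.1 may be left over from an edit, and the missing figure proves nothing, because a table can hold Kaplan-Meier output. That is plausible, but the written instruction still includes the 8.1 summary, and the protocol does not settle the matter.

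Three stronger readings are tempting and not supported:
- A reader might infer that the median will be 57 days whatever happens. That needs stable disease to start the clock, which the 7.7.7 formula lines do not support, and few patients continuing. Visit windows of ±3 days, dose delays and optional Part 2c assessments would scatter the value, and Cohort 1's assessment schedule is not visible.
- A reader might infer that visit spacing is a fault of the descriptive method alone. Kaplan-Meier event times fall on the same grid; at a true median of 42 days both methods give 57 in large samples.
- A reader might take this for a key endpoint. No section gives it that status, and protocol 10.1 makes every analysis exploratory.

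**Conclusion.** The point holds as a defect of specification with a predictable direction of error. Two incompatible methods are assigned to one table, and the descriptive one treats censored durations as complete, which biases median and mean downward. This follows from SAP 7.7.7 and 8.1 together and needs no simulation. The size depends on assumptions: in the responder-only illustration the median is about halved (360 to 182) and the mean falls by about 70% (519 to 154). Where stable disease counts and 0 to 20% continue after visit 9, a range suggested by the interim result and the planned response rate, the crude median stays near 57 days, while Kaplan-Meier is usually not reached once the true median is well beyond the visit 5 to visit 9 gap. With 20% continuing, that point comes later: half of the trials at 168 days and 86% at 336. The correction should be made, but no decision rule rests on this endpoint.

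**What to change.** In SAP 8.4.3, state that duration of response is estimated by Kaplan-Meier by treatment cohort, reporting the median with a complementary log-log 95% confidence interval and the numbers of events and of censored patients. Delete the reference to section 8.1 for this endpoint, and add a listing of individual durations with a censoring flag. Align protocol 10.8.2.3 when the protocol is next amended; protocol section 10 requires an amendment only for a change to a principal feature, so the SAP edit need not wait. The start states in the prose and formula lines of 7.7.7 should be reconciled in the same edit, because this change alone does not settle them.

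The cost is about a sentence of text and one listing; the method is already planned for overall and progression-free survival. The downsides are that the median may read 'not reached', and that Kaplan-Meier removes the censoring error but not the coarseness of the assessment grid.
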